6.2 Preparation/Handling/Storage/Accountability

Guidance and information on drug accountability for the investigational product will be provided to the site.

6.3 Measures to Minimize Bias: Randomization and Blinding

6.3.1 Method of Treatment Assignment

Subjects will be randomized in 1:1 allocation ratio to apremilast or placebo in a double-blind manner after meeting all randomization requirements.

Subject randomization for treatment assignments will be stratified according to a subject's rounded PPPASI total score ($\leq 20/21$ to $30/\geq 31$) at baseline and whether a subject has any focal infection at baseline (yes/no).

Protocol Number: 20200195

Date: 15 April 2022 Page 38 of 99

The randomization will be performed by and the randomization number will be provided by IRT.

The randomization date is to be documented in the subject's medical record and on the Subject Enrollment CRF.

6.3.2 Blinding

This is a double-blind study. Unblinding information consists of subject treatment assignments, including contents of investigational product boxes (eg, manufacturing lot number), and potentially unblinding data (PUBD) which has the potential to indicate treatment assignment for an individual subject. Unblinding information will be blinded to all subjects, site personnel, and Amgen as described below (Section 6.3.2.1 and Section 6.3.2.2).

The following assessments will be considered unblinding information:

- Apremilast pharmacokinetic assessments (Section 8.5)
- Apremilast biomarker assessments (Section 8.6)

6.3.2.1 Site Personnel Access to Unblinding Information

A subject's treatment assignment is to only be unblinded by the investigator when knowledge of the treatment is essential for the further management of the subject on this study or may potentially impact the safety of the subject. Unblinding at the study site for any other reason will be considered a protocol deviation. It is encouraged that the Amgen Trial Manager be notified before the blind is broken unless the investigator believes that identification of the study treatment is required for a medical emergency. If this is not possible, the Amgen Trial Manager must be notified within 24 hours after breaking the blind. The date and reason that the blind was broken must be recorded in the source documentation.

Unblinding information will not be accessible by investigative sites or subjects prior to the completion of the final analysis except for an emergency unblinding.

6.3.2.2 Access to Unblinding Information by Amgen or Designees

Preidentified members of the clinical study team will be unblinded in order to conduct the primary analysis (Section 9.4.1.2). Other members of the clinical study team will not have access to unblinding information until the completion of the final analysis.

6.4 Treatment Compliance

When subjects self-administer apremilast at home, compliance with the treatment will be assessed at scheduled visits and documented in the source documents and CRF.

Protocol Number: 20200195

Date: 15 April 2022 Page 39 of 99

6.5 Treatment of Overdose

For this study, any dose **4 times** greater than the treatment-specified dose within a 24-hour time will be considered an overdose.

In the event of an overdose, the investigator/treating physician should:

1. Contact the Amgen medical monitor immediately.

- 2. Evaluate adverse events associated with overdose and document them in the CRF.
- 3. Action will be taken for overdose associated adverse events if requested by the investigator or the Medical Monitor (determined on a case-by-case basis).
- 4. Document the quantity of the excess dose as well as the duration of the overdose in the CRF.

6.6 Prior and Concomitant Treatment

6.6.1 Prior Treatment

Prior therapies that were being taken/used for PPP (eg, topicals, systemics, phototherapy, etc.) within the last 5 years prior to randomization, will be collected. For prior therapies that were being taken for PPP, collect therapy name, dose, unit, frequency, route, start date and stop date, and reason for discontinuation. Prior focal infection and PAO therapies will be collected within the last 6 months (24 weeks) prior to randomization. For prior therapies that were being taken for focal infection and PAO, collect therapy name, indication, dose, unit, frequency, route, start date, and stop date. All other prior therapies that were being taken/used from 4 weeks prior to screening through the first dose of IP, will be collected. For all other prior therapies, collect therapy name, indication, dose, unit, frequency, route, start date, and stop date.

6.6.2 Concomitant Treatment

Throughout the study, investigators may prescribe any concomitant medications or treatments deemed necessary to provide adequate supportive care except for those listed in Section 6.1.4.

Concomitant therapies are to be collected from day 1 through the **30**-day post-treatment safety follow-up. For all other concomitant therapies, collect therapy name, indication, dose, unit, frequency, route, start date, and stop date.

Protocol Number: 20200195

Date: 15 April 2022 Page 40 of 99

7. Discontinuation of Study Treatment and Subject Discontinuation/Withdrawal

Subjects have the right to withdraw from investigational product and/or other protocol-required therapies, protocol procedures, or the study as a whole at any time and for any reason without prejudice to their future medical care by the physician or at the institution.

The investigator and/or sponsor can decide to withdraw a subject(s) from investigational product, device, and/or other protocol-required therapies, protocol procedures, or the study as a whole at any time prior to study completion for the reasons listed in Section 7.

7.1 Discontinuation of Study Treatment

Subjects (or a legally authorized representative) can decline to continue receiving investigational product and/or other protocol-required therapies and/or procedures at any time during the study but continue participation in the study. If this occurs, the investigator is to discuss with the subject the appropriate processes for discontinuation from investigational product or other protocol-required therapies and must discuss with the subject the possibilities for continuation of the Schedule of Activities (see Table 1-1) including different options of follow-up (eg, in person, by phone/mail, through family/friends, in correspondence/communication with other treating physicians, from the review of medical records) and collection of data, including endpoints, adverse events, and must document this decision in the subject's medical records. Subjects who have discontinued investigational product and/or other protocol-required therapies and/or procedures should not be automatically removed from the study. Whenever safe and feasible, it is imperative that subjects remain on-study to ensure safety surveillance and/or collection of outcome data.

Reasons for early removal from protocol-required investigational product(s) or procedural assessments may include any of the following:

- decision by Sponsor
- lost to follow-up
- death
- adverse event
- subject request
- lack of efficacy
- protocol deviation
- pregnancy

Protocol Number: 20200195

Date: 15 April 2022 Page 41 of 99

7.2 Subject Discontinuation/Withdrawal From the Study

Withdrawal of consent for a study means that the subject does not wish to receive further protocol-required therapies or procedures, and the subject does not wish to or is unable to continue further study participation. Subject data up to withdrawal of consent will be included in the analysis of the study, and where permitted, publicly available data can be included after withdrawal of consent. The investigator is to discuss with the subject appropriate procedures for withdrawal from the study and must document the subject's decision to withdraw in the subject's medical records. Subjects who are withdrawn or removed from treatment or the study will not be replaced.

If a subject withdraws from the study, he/she may request destruction of any samples taken and not tested, and the investigator must notify Amgen accordingly (see Section 11.6 for further details). Refer to the Schedule of Activities (Table 1-1) for data to be collected at the time of study discontinuation and follow-up and for any further evaluations that need to be completed.

7.2.1 Reasons for Removal From Study

Reasons for removal of a subject from the study are:

- · decision by sponsor
- withdrawal of consent from study
- death
- lost to follow-up

7.3 Lost to Follow-up

A subject will be considered lost to follow-up if he or she repeatedly fails to return for scheduled visits and is unable to be contacted by the study site.

The following actions must be taken if a subject fails to return to the clinic for a required study visit:

- The site must attempt to contact the subject and reschedule the missed visit as soon
 as possible and counsel the subject on the importance of maintaining the assigned
 visit schedule and ascertain whether or not the subject wishes to and/or is able to
 continue in the study.
- In cases in which the subject is deemed lost to follow-up, the investigator or
 designee must make every effort to regain contact with the subject (where possible,
 3 telephone calls and, if necessary, a certified letter to the subject's last known
 mailing address or local equivalent methods). These contact attempts are to be
 documented in the subject's medical record.
- If the subject continues to be unreachable, he/she will be considered to have withdrawn from the study with a primary reason of lost to follow-up.

Protocol Number: 20200195

Date: 15 April 2022 Page 42 of 99

For subjects who are lost to follow-up, the investigator should search publicly
available records where permitted to ascertain survival status. This ensures that the
data set(s) produced as an outcome of the study is/are as comprehensive as
possible.

If the subject has missed more than 1 visit, and the actions above have been taken to contact the subject, then the subject will be considered lost to follow up.

Protocol Number: 20200195

Date: 15 April 2022 Page 43 of 99

8. Study Assessments and Procedures

Study procedures and their time points are summarized in the Schedule of Activities (see Table 1-1).

If an enrolled subject is subsequently determined to be ineligible for the study, this must be discussed with the sponsor immediately upon occurrence or awareness to determine if the subject is to continue or discontinue study treatment.

Adherence to the study design requirements, including those specified in the Schedule of Activities, is essential and required for study conduct.

8.1 General Study Periods

8.1.1 Screening, Enrollment, and/or Randomization

Informed consent must be obtained before completing any screening procedure or discontinuation of standard therapy for any disallowed therapy. After the subject has signed the informed consent form, the site will register the subject in the IRT and screen the subject in order to assess eligibility for participation. The screening window is up to 4 weeks.

All screening evaluations must be completed and reviewed to confirm that potential subjects meet all eligibility criteria. The investigator will maintain a screening log to record details of all subjects screened and to confirm eligibility or record reasons for screening failure, (see Section 5.4) as applicable.

If a subject has not met all eligibility criteria at the end of the screening period, the subject will be registered as a screen fail. Screen fail subjects may be eligible for re-screening 1 time.

Rescreen subjects must first be registered as screen failures in IRT and subsequently registered as rescreens. Once the subject is registered as rescreened, a new 4-week screening window will begin. Subjects will retain the same subject identification number assigned at the original screening. If the rescreening period begins more than 30 days after the original signing of the informed consent form, all screening procedures, including informed consent, must be repeated.

8.1.2 Treatment Period

Visits will occur per the Schedule of Activities (Table 1-1). On-study visits may be completed as specified in the Schedule of Activities. The date of the first dose of apremilast is defined as day 1. All subsequent doses and study visits will be scheduled

Protocol Number: 20200195

Date: 15 April 2022 Page 44 of 99

based on the day 1 date. Apremilast is to be administered during each visit that it is required.

8.1.3 Safety Follow-up

Upon permanent discontinuation from the study treatment for any reason, a safety follow-up visit will be performed approximately **30 days** (+ **7** days) after the end of the last dose of apremilast.

8.1.4 End of Study

A subject is considered to have completed the study if he/she has completed all periods of the study including the last scheduled procedure / last follow up shown in the Schedule of Activities (Table 1-1).

8.2 General Assessments

8.2.1 Informed Consent

All subjects or their legally authorized representative must sign and personally date the IRB/IEC approved informed consent before any study-specific procedures are performed.

8.2.2 Demographics

Demographic data collection including sex, age, race, and ethnicity will be collected in order to study their possible association with subject safety and treatment effectiveness. Additionally, demographic data will be used to study the impact on biomarkers variability and pharmacokinetics of the protocol-required therapies.

8.2.3 Medical History

The Investigator or designee will collect a complete medical history that started within 5 years prior to enrollment through screening. Medical history will include information on the subject's concurrent medical conditions. Record all findings on the medical history CRF. In addition to the medical history above, PPP history must date back to the original diagnosis. The current severity will be collected for each condition that has not resolved.

8.2.4 Physical Examination

Physical examination will be performed as per standard of care. Physical examination findings should be recorded on the appropriate CRF (eg, medical history, event).

Protocol Number: 20200195

Date: 15 April 2022 Page 45 of 99

8.2.5 Physical Measurements

Height [in centimeters] should be measured without shoes. Weight [in kilograms] should be measured without shoes. Body Mass Index should be calculated using the following formula: BMI (kg/m^2) = weight $(kg)/[height (cm)/100]^2$.

8.2.6 Substance Abuse History

Obtain a detailed history of prior and/or concurrent use of tobacco.

8.3 Efficacy Assessments

8.3.1 Subject and Physician-reported Outcomes/ Quality of Life Measurements

8.3.1.1 Palmoplantar Pustulosis Area and Severity Index (PPPASI)

PPPASI is a disease-specific efficacy assessment tool used by Investigators established to detect a change of disease status on palms or soles (Section 11.8). As sub-scores right/left palm and right/left sole are evaluated for 3 signs of the disease (erythema, pustules/vesicle and desquamation/scale).

PPPASI produces numeric scores that can range from 0 to 72. A higher score indicates more severe disease.

8.3.1.2 Palmoplantar Pustulosis Severity Index (PPSI)

PPSI is a disease-specific efficacy assessment tools by Investigators (Section 11.9). This is established to detect a change of disease status on a specified palm or sole. Evaluated skin lesion is identified by either palms or soles, which has the most severe skin lesion at baseline.

PPSI produces numeric scores that can range from 0 to 12. A higher score indicates more severe disease.

8.3.1.4 Pruritis and Pain/Discomfort Assessment with Subject Visual Analogue Scale (VAS) for PPP Symptoms

Subjects will use VAS (with scores ranging from 0 to 100, with 100 being most severe) to assess the degree of PPP pain/discomfort and pruritus on the hands and feet (Section 11.11).

Protocol Number: 20200195

Date: 15 April 2022 Page 46 of 99

8.3.1.5 Dermatology Life Quality Index (DLQI)

DLQI is a skin disease-specific Quality of Life (QoL) questionnaire comprised of 10 items assessing the subject's status over the previous week (Section 11.12). DLQI can be used to assess 6 different aspects that may affect QoL: symptoms and feelings, daily activities, leisure, work, or school performance, personal relationships, and treatment. A numeric score ranging from 0 to 30 is produced with higher scores indicating increased disease severity.

8.4 Safety Assessments

Planned time points for all safety assessments are listed in the Schedule of Activities see (Table 1-1).

8.4.1 Vital Signs

The following measurements must be performed: systolic/diastolic blood pressure, heart rate, respiratory rate, and temperature. If abnormalities are found and they are considered to be an adverse event, record on the event CRF.

8.4.2 Clinical Laboratory Assessments

Refer to Section 11.2 for the list of clinical laboratory tests to be performed and to the Schedule of Activities (Table 1-1) for the timing and frequency.

The investigator is responsible for reviewing laboratory test results and recording any clinically relevant changes occurring during the study in the Events CRF. The investigator must determine whether an abnormal value in an individual study subject represents a clinically significant change from the subject's baseline values. In general, abnormal laboratory findings without clinical significance (based on the investigator's judgment) are not to be recorded as adverse events. However, laboratory value

Protocol Number: 20200195

Date: 15 April 2022 Page 47 of 99

changes that require treatment or adjustment in current therapy are considered adverse events. Where applicable, clinical sequelae (not the laboratory abnormality) are to be recorded as the adverse event.

All protocol-required laboratory assessments, as defined in Section 11.2, must be conducted in accordance with the laboratory manual and the Schedule of Activities (Table 1-1).

8.4.3 Suicidal Risk Monitoring

Apremilast treatment is associated with increased depression adverse reactions. Prior to apremilast use in subjects with a history of depression and/or suicidal thought or behavior, the Investigator should carefully weigh apremilast treatment risks and benefits. Evaluation of suicidal ideation and treatment-emergent suicidal ideation, new or worsening psychiatric symptoms will be assessed at scheduled visits during the study. Subjects should be advised to be alert for the emergence and/or worsening of depression, suicidal thoughts, or mood changes. Should any changes occur, the Investigator should be contacted.

If a subject suffers from new and/or worsening psychiatric symptoms, suicidal ideation, or attempt suicide, subject treatment discontinuation is recommended. Any time suicidal thoughts or suicide attempts are identified, the need for psychiatrist referral and any other pertinent actions (including treatment discontinuation) should be evaluated. Psychiatric evaluation results should be recorded in the CRF.

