4.1 Overall Design

The overall study design is described by a study schema in Section 1.2. The endpoints are defined in Section 3.

Approximately 170 subjects will be enrolled in the study, with subjects being randomized in a 1:1 ratio to 1 of 2 treatment arms: apremilast 30 mg BID or placebo. Subject

Protocol Number: 20200195

Date: 15 April 2022 Page 27 of 99

randomization will be stratified by a subject's rounded PPPASI total score (≤ 20/ 21 - 30/≥ 31) at baseline and baseline focal infection status (yes/no).

Randomized subjects will receive either apremilast 30 mg BID or placebo for 16 weeks, the duration of the double-blind placebo-controlled treatment period. During the active treatment period (week 16 to week 52), all subjects will receive apremilast 30 mg BID. The dose titration procedure (in line with the label) will be implemented for all subjects over a 5-day period at week 0 (the beginning of the double-blind placebo-controlled treatment period) and at week 16 (the beginning of the active treatment period) to mitigate potential gastrointestinal side effects and to maintain blinding.

After the final dose treatment, subjects will enter a **30-day** safety follow-up period. The total study duration per subject is **approximately** 60 weeks.

The primary analysis will be performed after the last subject has completed the week 16 visit (visit 8) or study discontinuation. An additional analysis will be conducted after all subjects have completed the week 24 visit (visit 10) or have been discontinued from the study. The final analysis will be conducted after all subjects have either completed or discontinued the study.

Approximately 45 sites in Japan are planned to participate in the study. Sites that do not enroll a subject within 6 months of site initiation may be closed.

Participants in this clinical investigation shall be referred to as "subjects". For the sample size justification, see Section 9.2.

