- Has a prior medical history of suicide attempt at any time in the subject's lifetime prior to signing of informed consent or randomization, or major psychiatric illness

Protocol Number: 20200195

Date: 15 April 2022 Page 32 of 99

requiring hospitalization within the last 3 years prior to signing of informed consent

Subject likely to not be available to complete all protocol-required study visits or procedures, and/or to comply with all required study procedures (eg, Clinical Outcome Assessments) to the best of the subject and investigator's knowledge

227 History or evidence of any other clinically significant disorder, condition or disease (with the exception of those outlined above) that, in the opinion of the investigator or Amgen physician, if consulted, would pose a risk to subject safety or interfere with the study evaluation, procedures or completion

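### Any suicide attempt before randomization bars entry, but after an on-study attempt stopping treatment is only recommended, and no rule prevents a first apremilast dose at week 16

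*Protocol*

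**What the plan says.** - **Entry.** One exclusion criterion in Protocol 5.2 reads "Has a prior medical history of suicide attempt at any time in the subject's lifetime prior to signing of informed consent or randomization". The opening of Section 5 rules out waivers of enrollment criteria.
- **On-study event.** Protocol 8.4.3 first notes that apremilast is linked to more depression reactions. It then gives one response to new or worsening psychiatric symptoms, to ideation and to an attempt: "suicidal ideation, or attempt suicide, subject treatment discontinuation is recommended". The next sentence says that whenever suicidal thoughts or an attempt come to light, the need for psychiatric referral and other measures, stopping treatment among them, should be evaluated. Footnote i to Table 1-1 repeats this and points back to 8.4.3.
- **Before apremilast use.** For subjects with a history of depression or of suicidal thought or behavior, 8.4.3 says "the Investigator should carefully weigh apremilast treatment risks and benefits".
- **Switch.** Protocol 4.1: "During the active treatment period (week 16 to week 52), all subjects will receive apremilast 30 mg BID".
- **Stopping treatment.** Protocol 7.1: "Reasons for early removal from protocol-required investigational product(s) or procedural assessments may include any of the following". The list names adverse event but not suicide attempt. The opening of Section 7 adds a power: "The investigator and/or sponsor can decide to withdraw a subject(s) from investigational product". For subjects who stop, 7.1 says "it is imperative that subjects remain on-study to ensure safety surveillance and/or collection of outcome data" whenever this is safe and feasible.
- **Unblinding.** Protocol 6.3.2.1 lets the investigator break the blind when knowing the treatment is "essential for the further management of the subject on this study or may potentially impact the safety of the subject".

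**The concern.** The plan judges a past suicide attempt, however long ago, serious enough to keep a person off this drug in this trial. An attempt during the trial is more recent and at least as relevant. Yet the plan leaves the response to the investigator and handles it in the same sentence as a worsening mood symptom.

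The week 16 switch adds a second issue. For a placebo subject it is the first exposure to apremilast, so it resembles a new enrollment. The entry exclusion, however, looks only at the time before consent or randomization and is not applied again.

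What is at stake is the safety of the individual subject, because the event could be fatal. No bias in the week 16 comparison is alleged.

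**Working it through.** No arithmetic applies: the plan states no figure on this point and the claim rests on none. The check is whether any text, read with the rest, compels a stop.

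1. **Does the entry exclusion reach a later attempt?** No. It is limited to attempts before consent or randomization. Section 8 requires discussion with the sponsor when an enrolled subject is later found ineligible, but an attempt after randomization does not make the subject ineligible under that criterion, so it does not clearly trigger that step.
2. **Does 8.4.3 compel a stop?** No. One sentence recommends stopping and the next asks for stopping and referral to be evaluated.
3. **Does Table 1-1 compel a stop?** No. Footnote i mentions discontinuation as required in 8.4.3, but 8.4.3 requires none. The table marks the eligibility check at screening; some criteria in 5.1 and 5.2 also apply at baseline, and none is re-applied at week 16. A psychiatric evaluation is scheduled at every visit, week 16 included, with no consequence fixed in advance.
4. **Does Section 7 compel a stop?** No. The list in 7.1 is permissive, and the power to withdraw a subject is something the investigator or sponsor can use.
5. **Does the switch text carry a condition?** No. The synopsis and 4.1 send all subjects to apremilast without a psychiatric proviso.
6. **Do the other safety provisions compel a stop?** No. Under 8.4.4.1.2 serious events reach the sponsor within 24 hours. SAP 9.6.2 summarizes suicide-related events, including the action taken with treatment. These inform a decision but do not make it.
7. **Who decides at week 16?** Normally a blinded investigator. Section 4.1 has all subjects go through titration at week 16 to protect the blind, so the investigator would not know whether this is a first exposure unless the blind is broken under 6.3.2.1.

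Two courses therefore stay within the protocol, provided the evaluation and the weighing have been done:

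- an attempt on placebo before week 16, followed by a first apremilast dose at week 16;
- an attempt on apremilast in either period, followed by continued apremilast.

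Both need the investigator to depart from the recommendation and the sponsor not to step in.

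**The case against.** The strongest reply is that this is supervised clinical discretion, not a missing control. The stop recommendation applies in both arms, and if it is followed the subject never reaches the switch. Every attempt prompts its own evaluation of referral and stopping. The instruction to weigh risk and benefit before apremilast use can fairly be read to cover a placebo subject at week 16, who by then has a history of suicidal behavior. Suicidality also gets more attention than most exclusions: its own section, an evaluation at every visit and an explicit stop recommendation. All of this stands, and it is why the harmful path is unlikely. It does not turn any of these provisions into a bar.

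Two stronger readings are tempting, and the documents do not support them.

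- *That the protocol contradicts itself, because Appendix 5 (Section 11.5) makes pregnancy and breastfeeding mandatory stops.* That contrast is selective. Malignancy, unstable cardiovascular disease, active tuberculosis and detected hepatitis B or C virus are also exclusions in 5.2, and none has a specific mandatory stop if it arises on study. Pregnancy and breastfeeding also involve exposure of a fetus or infant. They show that the protocol can write a mandatory stop, not that it had to write one here.
- *That the risk can be expressed as a probability.* One could assume an annual risk and compute the chance of at least one attempt among the 85 planned placebo subjects by week 16. That would be the chance of any attempt, not of the harm. The harm also needs the recommendation to be overridden without sponsor intervention, and the documents give neither rate.

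**Conclusion.** The point holds as a narrow patient-safety gap. Before randomization an attempt is an absolute bar. Afterwards it leads to a recommendation, an evaluation and a weighing of risks, none of which is a mandatory stop, and the week 16 switch has no condition of its own.

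The size is not quantified because the documents give no event rate. The event is expected to be rare, and the harmful path rarer still. What justifies acting is the gravity of the possible outcome and the small cost of closing the gap.

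The conclusion rests on reading the 8.4.3 wording (recommended, should) in its ordinary, non-binding sense, and on no site instruction outside these documents imposing a stop. A reader might infer that suicidality is unmonitored or that the primary result is affected. Neither follows from the text.

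**What to change.** In Protocol 8.4.3 and 7.1, state three things:

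- investigational product must be permanently discontinued after a suicide attempt on study, in either treatment period;
- apremilast must not be started at week 16 in a subject who has attempted suicide since randomization;
- the subject stays in study follow-up, as 7.1 already asks.

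Keep the present recommendation, with evaluation and referral, for ideation and for new or worsening psychiatric symptoms. The psychiatric evaluation already scheduled at week 16 can serve as the check before dispensing.

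The cost is wording in a protocol amendment, with its usual ethics review, and a letter to sites. No visit, test or staff is added. No analysis rule changes: SAP 9.5.1 and 9.5.2 already treat a stop for an adverse event before week 16 as a treatment failure, and SAP 9.1 plans no between-group comparison after week 16. The real downside is that the investigator loses discretion for this one rare event, including where continuing might have been judged best for the subject.
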